### **5.12.2 Fungal prophylaxis during neutropenia**

During periods of neutropenia patients should receive fungal prophylaxis. Recommended treatment is: isavuconazole due to drug interactions with glasdegib for absolute neutrophil count <500/mcl. Alternate prophylactic regimens are up to individual investigator's discretion.

## **5.13 Permitted concomitant therapy**

Growth factors including granulocyte colony-stimulating factors and granulocyte-macrophage colony-stimulating factors are permitted and should be used based on American Society of Clinical Oncology guidelines.

#### **5.14 Prohibited concomitant therapy**

Antineoplastic agents other than CPX-351, Glasdegib and hydroxyurea prior to the start of the study are not allowed.

Glasdegib can lead to QTc prolongation. Therefore, drugs that can prolong QTc should be avoided. Please refer to list of drugs in Appendix D.

Caution must be taken with moderate/strong CYP3A4/5 inhibitor in conjunction with Glasdegib. If possible, it is best to avoid the combination. If this is not possible, then QTc monitoring is recommended.

When there is an urgent need to start a moderate/strong CYP3A4/5 inhibitor or TdP drug, administration of these medications should not be delayed, the Investigator should consider temporarily interrupting Glasdegib dosing and should implement these additional monitoring procedures as soon as it is reasonably possible.

### **6.0 Toxicities and Dosing Delays/Dose Modifications**

---

Any patient who receives treatment on this protocol will be evaluable for toxicity. Each patient will be assessed for the development of toxicity according to the NCI Common Toxicity Criteria for Adverse Events (CTCAE), version 5.0. Dose adjustments should be made according to the system showing the greatest degree of toxicity.

#### **6.1 CPX-351 dose modification**

The dose of CPX-351 should not be modified. The dose can be delayed due to prolonged cytopenias or due to infections at any time.

CPX-351 should remain the same dose for entire cycle. For subsequent cycles, if body surface area (BSA) change is  $\geq 10\%$ , then the dose should be recalculated using the new BSA. If BSA remains  $< 10\%$  of baseline BSA (at time of screening), then dose of CPX-351 should not change and is calculated using baseline BSA

#### **6.2 Glasdegib dose modification for non-hematologic toxicities**

If a grade 3 non-hematologic toxicity occurs, interrupt the treatment until symptoms reduce or return to baseline. Resume Glasdegib at the same dose level if the event is not attributable to the study drug as determined by the Investigator. If the investigator deems the event as being possibly related to the study drug, then reduce the dose in increments of 25 mg. If a dose reduction is necessary after 50 mg, then the study treatment should be discontinued.

#### **6.3 Glasdegib dose modification for hematologic toxicities**

The dose of Glasdegib should not be modified for any hematologic toxicities.

#### **6.4 Glasdegib dose modification for QTc prolongation**

The dose of Glasdegib should be modified if there is evidence of QTc prolongation.

If the QTc is found to be between 480 to 500 ms, the recommendations are as follows:

- Correct any electrolyte abnormalities
- Review and adjust any medications that may be contributing to QTc prolongation. Refer to Appendix D for medications that are associated with QTc prolongation.
- Monitor ECG at least weekly for two weeks following resolution of the QTc prolongation to less than 480 ms
- If the QTc is found to be greater than 500, the recommendations are as follows:
  - Correct any electrolyte abnormalities
  - Review and adjust any medications that may be contributing to QTc prolongation
  - Interrupt Glasdegib
  - Resume Glasdegib at a reduced dose of 50 mg once daily when QTc is less than 480 ms or if the QTc returns to within 30 ms of baseline
  - Monitor ECG at least weekly for two weeks following resolution of the QTc prolongation to less than 480 ms
  - Consider re-escalating the dose to 100 mg daily if an alternative etiology for QTc prolongation is identified
- If QTc interval prolongation is associated with life-threatening arrhythmia, then Glasdegib should be discontinued permanently.

## **7.0 STUDY PROCEDURES**

---

### **7.1 Screening/Baseline Procedures**

Assessments performed exclusively to determine eligibility for this study will be done only after obtaining informed consent. Assessments performed for clinical indications (not exclusively to determine study eligibility) may be used for baseline values even if the studies were done before informed consent was obtained.

All screening procedures must be performed within 28 days prior to registration unless otherwise stated. The screening procedures include:

#### **7.1.1 Informed Consent**

A complete description of the study is to be presented and discussed with each potential subject or the subject's legally authorized representative, if applicable, and a signed and dated informed consent form is to be obtained before any study specific procedure is performed. A copy of the signed and dated consent form should be given to the subject before participation in the study.

The initial informed consent form, any subsequent reviewed written informed consent form and any written information provided to the subject must receive the IRB approval in advance of use. The subject should be informed in a timely manner if new information become available that may be relevant to the subject's willingness to continue participation in the trial. The communication of the information will be provided and documented via a revised consent form that captures the subject's dated signature. The informed consent will adhere to IRB requirements, applicable laws and regulations and sponsor requirements.

#### **7.1.2 Medical history**

Complete medical, surgical and oncology history as well as history of infections are obtained at screening. Any changes from Screening (e.g. worsening severity or abnormal findings) are considered to be adverse events (AEs).

### **7.1.3 Demographics**

Demographic profile will include date of birth, gender, race, and ethnicity.

### **7.1.4 Review subject eligibility criteria**

At the initiating site, the information below must be reviewed with the initiating site PI and research manager prior to the assignment of the subject study ID and initiation of treatment. For participating sites, the following information must be redacted of any patient identifiers and sent at least 3 business days prior to the planned start date of treatment for eligibility confirmation and subject ID assignment to [[contact]](mailto:[contact]) via secure email:

- Signed informed consent
- Signed eligibility checklist
- Bone marrow biopsy report
- Physical exam including ECOG and medical history
- All screening labs
- Baseline ECG

Review of eligibility criteria, as described in Section 3, is required to ensure subject qualification for study entry.

The signed eligibility checklist, redacted source documentation as mentioned above and signed informed consent for each enrolled patient must be emailed to [[contact]](mailto:[contact]) per section 4.1.

### **7.1.5 Review previous and concomitant medications**

All concomitant medications taken by the subject during the study are to be recorded up until 28 days after last study dose. If a reportable adverse event occurs within 28 days after last study dose, recording of concomitant medications should continue until resolution of adverse event.

### **7.1.6 Physical exam including vital signs, height and weight**

Vital signs (temperature, pulse, respirations, blood pressure), height, weight will be collected at screenings and during each physical exam. Subjects will be examined by an investigator during study visits. (Note: height is only required at screening.)

### **7.1.7 Performance status**

The Eastern Cooperative Oncology Group (ECOG) Performance status will be evaluated prior to study entry, on day 1 of induction and day 28 of induction, on day 1 and day 28 of each subsequent consolidation cycles, and on day 1 of each cycle of maintenance. (See appendix A)

### **7.1.8 Hematology**

Hematology to include hemoglobin (Hgb), platelets, total white blood cell count (WBC), and differential.

### **7.1.9 Serum chemistries**

Comprehensive metabolic panel (CMP) to include: albumin, alkaline phosphatase, ALT/SGPT, AST/SGOT, BUN, creatinine, electrolytes (sodium, potassium, calcium, chloride, bicarbonate), glucose, and total bilirubin. Additional chemistries: lactate dehydrogenase (LDH), phosphate, magnesium, and uric acid.

#### **7.1.10 Coagulation**

Coagulation profile includes International Normalized Ratio (INR), prothrombin time (PT) and activated partial thromboplastin time (PTT).

#### **7.1.11 ECG**

Resting 12-lead ECG will be taken at screening.

#### **7.1.12 Echocardiogram**

An ECHO should be performed during screening before starting treatment with CPX-351.

#### **7.1.13 Urinalysis**

Standard urinalysis dipstick assessment (pH, protein, glucose, blood, ketones, and leukocytes) should be performed.

#### **7.1.14 Pregnancy test (for females of child bearing potential)**

Serum or urine beta HCG test are acceptable and should be done prior to starting treatment. Sites should follow local institutional guidelines.

#### **7.1.15 Bone marrow procedures**

Bone marrow aspirate and biopsy should be done during screening. It should be completed within 28 days. Cytogenetic and molecular profiling will be analyzed with these samples.

#### **7.1.16 Research samples**

Additional bone marrow aspirate or peripheral blood will be collected for gene expression testing.

### **7.2 Procedures during Treatment**

#### **7.2.1 Induction**

- Physical exam will be done weekly
- Review previous and concomitant medications
- ECOG Performance Status Review
- Blood draws for laboratory studies will be done weekly
- ECGs will be done on day 6 before starting Glasdegib and approximately one week after day 6 (on day 13-15)
- Review of concomitant medications
- Adverse event assessment
- Assessment of minimal residual disease assessed by multi-parameter flow cytometry. This should be done according to local institutional guidelines.

- Bone marrow aspiration and biopsy
  - Day 20
  - Upon recovery of cytopenias typically around day 28 to 60, at the discretion of treating physician. If counts has not recovered by day 60, then complete on day 60.
- Additional BMA or PB will be collected for gene expression testing

### **7.2.2 Rationale for the timeline of bone marrow assessments**

During the phase II and III trials with CPX-351, there was evidence of relatively delayed clearance of bone marrow blasts compared to standard induction chemotherapy. Therefore, bone marrow assessments should be performed on day 20, in order to avoid labeling a patient as requiring re-induction if the bone marrow biopsy is done on day 14 inadvertently.

Similarly, the subsequent bone marrow should be delayed until there is evidence of normal hematopoiesis between days 28-60. The exact day to perform the bone marrow assessment is at the discretion of the treating physician. It is strongly encouraged to avoid performing the bone marrow biopsy prematurely. If peripheral counts do not recover by day 60, bone marrow should be performed to assess the status of the disease.

### **7.2.3 Adequacy of bone marrow specimen**

An adequate bone marrow specimen is required to evaluate for remission (during induction days 28-60). An adequate bone marrow specimen is defined as having nucleated cells in the aspirate with spicules. The nucleated cell count is determined by the pathologist and the presence of spicules can be determined by the provider performing the bone marrow biopsy at the time of obtaining the aspirate. If the sample is inadequate, the bone marrow should be repeated within one week. In case of a dry tap without any aspirate, two cores are preferred; however, local institutional guidelines should be followed.

### **7.2.4 Bone marrow blasts of 5-10%**

In the case of the bone marrow specimen has 5-10% blasts on bone marrow obtained prior to induction day 46, it is encouraged to reassess the marrow in 1-2 weeks (no later than day 60), instead of labeling the patient as not in remission. This will allow more time for the relatively delayed effects of CPX-351. The final decision is at the discretion of the treating physician.

### **7.2.5 Assessment of remission status**

The date of CR and CRi or relapse is based on the date of the bone marrow biopsy that was performed. The exact date of achievement of CR is based on the date when the bone marrow biopsy demonstrates less than 5% blasts with the peripheral ANC  $\geq 1,000/\mu\text{L}$  and the platelet count  $\geq 100,000/\mu\text{L}$ . If the bone marrow biopsy shows less than 5% blasts prior the day the peripheral counts recover, then the date of CR is based on the date when the peripheral counts recover.

### **7.2.6 Reinduction**

- Prior to reinduction, an ECHO should be completed
- Review of concomitant medications
- Adverse event assessment
- ECOG performance status

- Physical exam will be done weekly
- Blood draws for laboratory studies will be done weekly
- ECGs will be done within 24 hours of day 4 before starting Glasdegib
- For females with childbearing potential, a pregnancy test will be done
- Assessment of minimal residual disease assessed by multi-parameter flow cytometry. This should be done according to local institutional guidelines.
- Bone marrow aspiration and biopsy
  - Day 20
  - Upon recovery of cytopenias typically around day 28 to 60, at the discretion of the physician. If counts has not recovered by day 60, then complete on day 60.
- Additional BMA or PB will be collected for gene expression testing

### **7.2.7 Consolidation**

- Physical exam will be done weekly
- Review of concomitant medications
- Adverse event assessment
- Blood draws for laboratory studies will be done weekly
- For females with childbearing potential, a pregnancy test will be done
- ECOG performance status
- ECGs will be done on within 24 hours of day 4 of every cycle
- Adverse event assessment
- Bone marrow at the end of consolidation is recommended but is not required by the study.

### **7.2.8 Maintenance**

- Physical exam will be done on day 1 of every cycle
- Review of concomitant medications
- Adverse event assessment
- ECOG performance status
- Blood draws for laboratory studies will be done on day 1 of every cycle
- For females with childbearing potential, a pregnancy test will be done

### **7.3 End of Treatment Visit**

All subjects will undergo an end of treatment evaluation. End of study is defined as at least 12 months after the final subject is enrolled, or sooner if all subjects have died, discontinued the study, are lost to follow-up, or withdrew consent prior to the two years after the last subject is enrolled.

- Physical exam
- Review of concomitant medications
- Adverse event assessment
- ECOG Performance Status Review
- ECG will be done
- Blood draws for laboratory studies
- Assessment of minimal residual disease assessed by multi-parameter flow cytometry. This should be done according to local institutional guidelines.
- Bone marrow aspiration and biopsy

- At any time of suspected relapsed disease, at the discretion of treating physician
- Additional BMA or PB will be collected for gene expression testing

#### **7.4 Follow-up Procedures**

Patients will be followed every 3 months for a minimum of one year after removal from or completion of treatment or death, whichever comes first. Patients who undergo allogeneic stem cell transplant will only be followed up for survival status. Patients removed from treatment for unacceptable adverse events will be followed until resolution or stabilization of the adverse event then for relapse and survival afterwards.

- Survival status (either in clinic during standard visit or by phone)
- Physical Exam
- ECOG Performance Status Review
- Blood draws for laboratory studies
- Bone marrow aspiration and biopsy
  - At any time of suspected relapsed disease, at the discretion of treating physician
- Assessment of minimal residual disease assessed by multi-parameter flow cytometry. This should be done according to local institutional guidelines.

#### **7.5 Correlative Studies**

In the non-intensive arm of the phase II trial with LDAC with Glasdegib, there were several genes that correlated with improved OS [11]. Lower levels of expression of FOXM1 and MSI2 and higher expression levels of BCL2 and CCND2 correlated with improved overall survival. In the intensive treatment arm with Glasdegib and cytarabine/daunorubicin, higher PTCH1 expression correlated with improved overall survival. Furthermore, in the intensive arm, mutations in FLT3, TP53, CEP170, NPM1 and ANKRD26 correlated with overall survival. Interesting to note, that patients with AML with mutated FLT3 (which is generally a poor risk group) did better than AML with wild type FLT3. Therefore, we will be measuring some of gene expression to see if this observation of their correlation with improved overall survival is confirmed.

Furthermore, we will be measuring MRD by MFC at the end of induction. University of Washington is the preferred facility who will receive the samples and assess MRD. If samples cannot be sent to University of Washington, sites should send their samples for MRD assessment according to their local institutional guidelines. We will determine if the status of MRD by MFC at the end of induction correlates with survival.

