## **10.2 Complete remission**

Complete remission is defined as no circulating blasts or extramedullary disease with a bone marrow biopsy with trilineage hematopoiesis with less than 5% blasts and ANC greater/equal than 1,000/uL and platelet count greater/equal than 100,000/uL.

Refractory disease is the failure to achieve CR at the end of induction.

Progressive disease is the increase of at least 25% in the absolute number of circulating or bone marrow leukemic blasts or appearance of extramedullary disease.

Relapsed disease is the reappearance of blasts in the bone marrow (greater than 5%) or in the blood after achieving CR or CRi.

MRD negative CR is the absence of detectable leukemic blasts using multiparameter flow cytometry at the University of Washington.

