## **10.4 Event-free survival**

Event-free survival is defined as the time from screening biopsy to the date of confirmed disease progression, relapse from CR/CRi, treatment failure, or death, whichever comes first. This was chosen as an endpoint for several reasons. It is known to incorporate several endpoints of interest including efficacy of the treatment as well as toxicity that both contribute to the outcome of the patient. Complete remission may not capture the full benefits of Glasdegib since the drug may prevent relapse through different mechanisms than enhanced cytotoxicity.

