## **10.5 Final Response Assessment**

Overall survival is measured as the time from the date of diagnostic biopsy which confirmed disease to the date of death from any cause. Patients not known to have died at last follow-up are censored on the date they were last known to be alive. Patients will be followed for a minimum of one year from the completion of the treatment.

Patients who go on to allogeneic transplant will be censored for survival on the dates that they start conditioning regimen to avoid transplant as a confounding factor in analysis of overall survival.

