### **13.4.2.3 Survival**

Time-to-event measures, such as, overall survival, time to normal hematopoiesis, duration of response, and influence of MRD status will be characterized by Kaplan-Meier methods, both overall and by strata of interest. Differences in times/survival between or among groups will be evaluated by the log-rank test. If assumptions are reasonably met, then Cox proportional-hazards models will be made to examine the effects on survival of covariates adjusting for other covariates. Ties in survival time will be broken by the subtracting a small, randomly generated amount from each tied observation (Borucka, 2014).

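### End-of-induction MRD is related to survival counted from the biopsy, with no landmark and no rule for deaths before the marrow; the MRD laboratory is also defined inconsistently

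*Combined protocol and SAP*

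**What the plan says.** **Aim.** Section 7.5 states the question: "We will determine if the status of MRD by MFC at the end of induction correlates with survival".

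**Timing of MRD.** Section 7.5: "Furthermore, we will be measuring MRD by MFC at the end of induction". The Schedule of Events lists MRD at the day-20 induction-response marrow, at the day 28 to 60 remission evaluation and at suspected relapse. Section 7.2.1 times the remission marrow as "Upon recovery of cytopenias typically around day 28 to 60, at the discretion of treating physician", and section 7.2.6 repeats both marrows after re-induction.

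**Start of the survival clock.** Section 10.5: "Overall survival is measured as the time from the date of diagnostic biopsy which confirmed disease to the date of death from any cause". Section 10.4 has the same feature: "Event-free survival is defined as the time from screening biopsy to the date of confirmed disease progression". The screening window in the Schedule of Events runs up to 28 days before day 1. Section 7.5 does not say which survival measure is meant.

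**Analysis.** Section 13.4.2.3 says that "influence of MRD status will be characterized by Kaplan-Meier methods", overall and by strata, with log-rank tests and possibly Cox models. It gives no landmark, time-dependent covariate or rule for patients without an MRD result. Section 13.4.2.1 allows secondary analyses on intent-to-treat, per-protocol and ad-hoc sets.

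**Laboratory.** Section 10.2: "MRD negative CR is the absence of detectable leukemic blasts using multiparameter flow cytometry at the University of Washington". The Study Summary and section 2.3 also name that laboratory. Section 7.5, however, says that if a sample cannot be sent there, "sites should send their samples for MRD assessment according to their local institutional guidelines". Section 9.2 permits a locally designated facility, and sections 7.2.1, 7.2.6, 7.3 and 7.4 refer MRD assessment to local guidelines.

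**The concern.** A patient can have an end-of-induction result only by living to that marrow. When the clock starts at the biopsy, the time before the marrow is survival that every tested patient is bound to have. Two consequences follow.

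First, the curves by MRD group sit too high if they are read as prognosis from the time MRD becomes known.

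Second, the comparison between groups is protected only if both groups carry the same guaranteed time. The plan does not say what happens to a patient who dies after day 20 but before the remission marrow. Such a patient could be left out, classed by the day-20 result, or placed with everyone who did not reach MRD-negative remission. The last two choices can put early deaths disproportionately in the non-negative group and make MRD look prognostic when it is not.

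The laboratory wording is a separate problem. Read literally, a patient tested locally with no detectable blasts cannot meet the section 10.2 definition, yet sections 7.5 and 9.2 allow that test. No common cut-off or analysis by laboratory is given.

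At stake is the credibility of an exploratory result that may inform later trials.

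**Working it through.** The plan gives no effect size, power or cut-off for the MRD analysis, so there is no planned figure to reproduce.

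**Inputs from the documents:** remission marrow on day 28 to 60; biopsy up to 28 days before day 1; 30 evaluable patients (13.3); median survival 9.5 months in the CPX-351 phase 3 arm (1.5.3). **Assumptions:** exponential survival from biopsy with that median; 14 days from biopsy to day 1; 18 months of follow-up; no transplant censoring.

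**1. Deaths before the marrow.** Rate λ = ln 2 / 9.5 = 0.0730 per month, with 30.4375 days per month. Share dead by day d after biopsy = 1 − exp(−λd/30.4375).

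| Days after biopsy | Dead | Of 30 |
|---|---|---|
| 28 | 6.5% | 1.9 |
| 60 | 13.4% | 4.0 |
| 88 (28 + 60) | 19.0% | 5.7 |
| 120 | 25.0% | 7.5 |

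**2. Guaranteed time in the curves.** One-year survival counted from the marrow is exp(−12λ) = 41.7%. Counted from biopsy among patients alive at a marrow a months after biopsy, it is exp(−λ(12 − a)).

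- Mid-window marrow (day 44), no lag: a = 44/30.4375 = 1.45 months, giving 46.3%, a gap of 4.6 points.
- With a 14-day lag (day 58): a = 1.91, giving 47.9%, a gap of 6.2 points.
- With 35% of patients re-induced 20 days later (average day 65): a = 2.14, giving 48.7%, a gap of 7.0 points.
- Extremes for a single patient: day 28 gives 44.6% (2.9 points) and day 88 gives 51.4% (9.8 points).

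**3. Comparison between groups with no true MRD effect.** I simulated 400,000 patients, with 35% re-induced, half MRD-negative at the last marrow, and MRD independent of survival. The variant doubles the death hazard through day 60 of treatment. The clock starts at the biopsy except in the last row.

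| Handling of patients who die before the marrow | HR, base | HR, doubled early hazard |
|---|---|---|
| Left out; tested patients only | 1.00 | 0.99 |
| Day-20 result used, 20% negative at day 20 | 0.89 | 0.82 |
| Same, 30% negative | 0.92 | 0.87 |
| Same, 40% negative | 0.96 | 0.93 |
| Same, 50% negative | 1.00 | 0.99 |
| Counted as not MRD-negative | 0.69 | 0.54 |
| Fixed landmark at day 81 | 1.00 | 0.99 |

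At N = 30, without re-induction (3,000 runs, nominal two-sided 5%):

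- Early deaths counted as not negative: HR 0.72, type I error 11.3%.
- Tested patients only, same timing in both groups: HR 1.00, type I error 5.6%.
- Tested patients only, one group tested about 20 days later: HR 0.94 or 1.08, in favour of the later-tested group, type I error about 5%.
- Risk sets starting at the MRD date: HR 1.00 to 1.01, type I error 5.0% to 5.8%, in every scenario.

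**4. Mixed laboratories.** Assume a true HR of 2.0 (positive versus negative), half MRD-positive, local sensitivity 70% to 85%, local specificity 90%, and errors unrelated to outcome. With local share f, overall sensitivity S = (1 − f) + f·Se and specificity Sp = (1 − f) + f·0.9. The observed HR is approximately (1 + PPV)/(2 − NPV), where PPV and NPV are the predictive values of the mixed result.

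For f = 0.5 and Se = 0.70: S = 0.85 and Sp = 0.95, so PPV = 0.425/0.450 = 0.944 and NPV = 0.475/0.550 = 0.864. The observed HR is 1.944/1.136 = 1.71. Across the assumed range it is 1.87 to 1.92 with 20% local samples and 1.71 to 1.82 with 50%.

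**The case against.** A reader might infer that the planned analysis is biased as it stands. The documents do not support that. Section 7.5 names MRD at the end of induction, and the Schedule of Events separates the day-20 induction-response marrow from the later remission evaluation. No passage says that a day-20 value replaces a missing later one, or that early deaths are counted as not MRD-negative. On the plain reading both groups come from the same marrow, and the hazard ratio under no effect is about 1.0. The biased versions rest on groupings that the plan neither states nor excludes. The day-20 version also depends on an assumed negativity rate and vanishes when that rate equals the later one. All of this stands.

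A reader might also infer that local assays would create a false association. If errors are unrelated to outcome, they weaken the association. A directional bias would need the choice of laboratory to follow prognosis, and nothing in the documents shows that.

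The gap in one-year survival compares two different time spans, so it is a matter of interpretation and not a bias between MRD groups. That also stands.

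Finally, the practical weight is small. The objective is exploratory and section 13.4.2.1 treats p-values only as a guide. With an assumed 12 to 20 deaths in equal groups, the standard error of the log hazard ratio is 2/√20 = 0.45 to 2/√12 = 0.58, and power for a hazard ratio of 2 is only 22% to 34%.

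What the objection does not remove is that the harmful groupings remain open. Section 13.4.2.1 allows intent-to-treat sets, which include deaths before the marrow. The natural complement of the section 10.2 response category is everyone else, including those deaths.

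**Conclusion.** The point holds as a low-cost improvement to an exploratory analysis, not as a demonstrated bias. Starting the clock at the biopsy adds about 5 to 7 points to one-year survival in the MRD-group curves, compared with counting from the marrow. Whether the comparison is biased depends on an unstated rule: the null hazard ratio is about 1.0, 0.8 to 1.0, or 0.55 to 0.7 under the three possible groupings. These sizes rest on an assumed exponential 9.5-month median taken from an earlier trial, and on assumed lag, re-induction and day-20 negativity rates. The direction of the early-death effect follows from the time order alone.

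The conflict between the University of Washington definition and the permission for local assays is plain in the text and must be reconciled; its likely effect is dilution. The primary analysis of six-month event-free survival and its decision rule are untouched.

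**What to change.** In section 13.4.2.3:

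1. Define MRD status at the end-of-induction remission marrow (after re-induction, the remission marrow of that course), and state that a day-20 result does not stand in for it.
2. Count survival from that marrow, or from a fixed landmark day, among patients alive with a result by then. State which survival measure is used.
3. Report the number of patients who die before that point or have no result, and do not class them as MRD-positive or as not negative.
4. Reconcile the Study Summary and sections 2.3 and 10.2 with 7.2.1, 7.2.6, 7.3, 7.4, 7.5 and 9.2. Record the testing laboratory for each sample, and report the analysis with University of Washington results only and with all results.

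The cost is wording and one recorded data item. Patients who die before the landmark leave a comparison that starts with about 30: roughly 2 to 6 of them for a marrow 28 to 88 days after biopsy, and 7 or 8 by day 120, under the assumed median. The University of Washington-only analysis loses more. A fixed landmark also drops patients whose marrow comes later than the chosen day. The change does not address the censoring of overall survival at the start of transplant conditioning (section 10.5), which may itself depend on MRD status and should be kept in mind when the curves are read.
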